#### 5.9.1.3. Secondary Estimand – While on Treatment Strategy (ITTv5)

The Secondary Estimand is designed to answer the question on the treatment effect of HMTM dose of 16 mg/day as monotherapy versus control (containing a small amount of MTC, spiked) in the targeted population of subjects with probable AD and MCI-AD up to 52 weeks while on treatment, based on the two co-primary endpoints.

This estimand is constructed in line with ICH E9 (R1) addendum. The five components defining the estimand of interest are:

- A. Treatment:** Up to 52 weeks of HMTM dose of 16 mg/day or matching control (containing a small amount of MTC) as monotherapy.
- B. Population:** Subjects with probable AD and MCI-AD as described by the inclusion and exclusion criteria, randomized under protocol version 5.0 or higher.
- C. Patient-level outcomes / variables:** The co-primary outcomes are the change from Baseline of the ADAS-cog11 and ADCS-ADL23 at the end of treatment of up to 52 weeks (see Section 4.5.1)
- D. Population-level summary:** Population weighted least squares means difference.
- E. Intercurrent Events:** The following ICE have been identified which could prevent measurement of the primary outcome or change the interpretation of the measured primary outcome:
  1. A dose interruption for more than 14 consecutive days or more than two occasions of dose interruptions up to a maximum of 14 consecutive days due to safety concerns and initiated by the PI (see Section 4.4)
  2. Intercurrent illnesses and initiation of medical food or medications not allowed by protocol, identified during the BDRM
  3. Study treatment non-compliance, defined as <80% or >120% taking into consideration any dose interruptions (if this cannot be estimated, it does not automatically result in a non-compliance)
  4. Deaths before the completion of 52 weeks treatment phase

Sponsor:	TauRx Therapeutics Ltd.		
Protocol:	TRx-237-039		
Document Version No.:	3.0	Document Date:	07-JUN-2023

**Events 1, 2, and 3** that occur while on treatment will be handled according to a treatment policy strategy, using data after occurrence of the ICE.

**Events 4** will be handled as treatment failure. If the patient dies prior to Week 52, the missing assessment at the end of treatment will be imputed by the population average in decline at the end of treatment within the control arm.

#### 5.9.1.4. MRI Estimand (ITTv5)

The MRI Estimand is designed to answer the question on the treatment effect of HMTM dose of 16 mg/day as monotherapy versus control (containing a small amount of MTC) in the targeted population of subjects with probable AD and MCI-AD at Week 52, regardless of trial product discontinuation, based on the MRI whole brain volume.

This estimand is constructed in line with ICH E9 (R1) addendum. The five components defining the estimand of interest are:

- A. Treatment:** 52 weeks HMTM dose of 16 mg/day or matching control (containing a small amount of MTC) as monotherapy, regardless of adherence.
- B. Population:** Subjects with probable AD and MCI-AD as described by the inclusion and exclusion criteria, randomized under protocol version 5.0 or higher.
- C. Patient-level outcome / variable:** Annualized rate, defined as the absolute change from Baseline, of whole brain atrophy as measured by MRI and quantified using the Boundary Shift Integral (BSI) at Week 52.
- D. Population-level summary:** Population weighted least squares means difference.
- E. Intercurrent Events:** Identification and handling of ICE as described for the primary estimand (see Section 5.9.1.1), including the sensitivity analyses.

The MRI Estimand (ITT) is defined as the MRI Estimand, extending the population to the ITT population as done for the Primary estimand (ITT) (see Section 5.9.1.2).

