
Subjects willing to discontinue AChEI and/or memantine in order to take part in the study must be documented to be eligible according to clinical inclusion / exclusion criteria, screening MRI and amyloid positive PET scan, before these drugs are discontinued.

Only subjects with a CDR 0.5 will undergo F-FDG-PET. F-DG-PET images are to be obtained prior to Visit 2 (and at least 60 days after the last dose of AChEI and/or memantine) for purposes of establishing the baseline assessment. Completion of this scan must be confirmed prior to randomization; other than confirmation of acceptable quality, the results per se are not considered for eligibility at the Screening visit. The baseline

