The screening assessments should be performed so that MRI is the last of the key eligibility assessments to be scheduled. The screening MRI scan(s) results (of sufficient quality) must be available for the purpose of inclusion/exclusion review and confirmation of compliance with inclusion and exclusion criteria by an independent neuroradiologist. If the initial screening MRI is not of sufficient quality, then a repeat screening scan may be performed. If the repeat scan cannot be accomplished within the pertinent window (see Table 10-1), then the subject must be re-consented and re-screened. For subjects who are re-screened for other reasons and an acceptable MRI scan was already completed during the original Screening window, the scan does not require repetition. See Section 10.2 for a summary of alternate arrangements that may be implemented due to COVID-19.

In subjects receiving an AChEI and/or memantine at Screening, documentation of amyloid positive PET imaging (either by prior history or in the sequence of screening tests) and confirmation of compliance with inclusion and exclusion criteria by the independent neuroradiologist (inclusive of screening MRI), must be available prior to the discontinuation of such medication.

At any step, should any of the assessments indicate the subject's ineligibility, the screening process should be stopped immediately (no further assessments performed) and the subject considered a screen failure. The reason(s) for screen failure is (are) to be documented.

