  - Using adequate contraception (a barrier method [such as condom, diaphragm or cervical/vault cap] with spermicidal foam, gel, film, cream, or suppository; intrauterine device [IUD] or system, or oral or long-acting injected or implanted hormonal contraceptives for at least 90 days prior to Baseline; or vasectomized partner [with the appropriate post-vasectomy documentation of the absence of spermatozoa in the ejaculate]) or true abstinence (when this is in line with the preferred and usual lifestyle of the subject); subjects must be competent to use adequate contraception and to agree to continue to maintain adequate contraception throughout participation in the study (including up to 4 weeks after the last dose of study drug)
7. Subject and/or, in the case of reduced decision-making capacity, legally acceptable representative(s) (LAR(s)), consistent with local and national law, is able to read, understand, and provide written informed consent in the designated language of the study site
8. Has one (or more) identified adult study partner (*i.e.*, a caregiver or informant) who meets the following criteria:
  - Either lives with the subject, or in the investigator's opinion, the extent of contact is sufficient to provide meaningful assessment of changes in subject

behavior and function over time and provide information on safety and tolerability (*e.g.*, sees the subject on average for  $\geq 1$  hour/day  $\geq 3$  days/week)

- Is willing to provide written informed consent for his/her own participation
- Is able to read, understand, and speak the designated language(s) at the study site
- Agrees to accompany the subject to each study visit
- Is able to verify compliance with study drug

9. The subject must not have been taking either an AChEI, *i.e.*, donepezil, galantamine, or rivastigmine, and/or memantine, for at least 60 days at the time of the baseline assessments

- Subjects never previously treated with an AChEI and/or memantine may be enrolled if initiation of treatment with these medications is not planned for the time period during which the subject will be participating in this study

10. Able to comply with the study procedures in the view of the investigator

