### **12.3 Randomization**

Subjects will be randomized to one of three study regimens described in Section 12.2: LMTM 16 mg/day, LMTM 8 mg/day, or placebo (4:1:4, at the study level). Randomization will be stratified according to severity (three levels: MMSE 16-19, 20-25, or 26-27) at study level for those randomized to Protocol Version 5.0 and above, prior use of standard AD treatment (two levels: AChEI/memantine or none), and region (two levels: North America or Europe).

Enrollment will be such that subjects are assigned to the MMSE severity groups based on screening MMSE score with a target of approximately 2:3:1 (MMSE 16-19, MMSE 20-25, and MMSE 26-27, respectively) for those randomized to Protocol Version 5.0 and above; to achieve this target, enrollment will be monitored and controlled at the site level for high recruiting sites and capped as needed at the study level.

Randomization, stratification, and enrollment cap requirements will be controlled by a web-based RTSM system.

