#### 15.3.3.2 MRI

The screening MRI (to be obtained within the 9-week Screening period [Days -63 to -1] in subjects not receiving an AChEI and/or memantine, or Days -112 to -63 in subjects who begin Screening on an AChEI and/or memantine) will also be used as the baseline for volumetric measurements. The volumetric MRI will be repeated approximately every 13 weeks in the double-blind treatment period after randomization (*i.e.*, after 13, 26, 39, and 52 weeks) as well as after the additional 26 and 52 weeks of open-label treatment. For subjects who terminate early (in either the double-blind treatment or open-label treatment periods), if the subject's last MRI scan was performed  $<90$  days prior to the early termination date, no additional MRI scan is required.

Imaging assessments will be made by central readers as follows:

- Brain MRI will be evaluated for temporal and parietal, whole brain, lateral ventricular, hippocampal, putamen, nucleus accumbens, and nucleus basalis ROI volumes. Change in MRI volumetric parameters will be quantified by the imaging core laboratory.
- T2\*-weighted gradient-recalled echo is to be included to enable the detection and quantification of the image hyperintensities.
- SPM preprocessing may be performed, which involves registration of the MR images to atlas space, segmentation into tissue types (grey, white, cerebral spinal fluid). After database lock, the voxelwise change may be quantified in the segmented MR maps using an SPM approach (models to be characterized in the SAP). Details of analysis conducted will be reported in a separate report.

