## **17.4 Clinical Efficacy and Imaging Analysis**

The various analyses planned in the study are outlined below. The SAP will be more specific and clearly state which analysis and which model will be applied to what type of data.

Subjects will be analyzed in the treatment group and stratification to which they were randomized unless stated otherwise in potential sensitivity analyses. For safety analyses, treatment assignment will be based on the treatment actually received. If a subject receives an incorrect treatment transiently, he/she will be assigned to the predominant treatment group (*i.e.*, the treatment group for which he/she received the greatest number of doses).

For E-MITT, MI-MITT, and PI-MITT analyses, only valid data will be included in the primary and secondary analyses. In subjects who have initiated treatment with an AChEI and/or memantine, assessments made after initiation of such treatment are not considered valid as they could confound the interpretation of the results and will be excluded. Such subjects and affected assessments will be identified prior to unblinding. Sensitivity analyses will be provided for the primary and selected secondary analyses including all data.

The primary and key secondary analyses will be further restricted by excluding subjects who were randomized under protocols prior to Protocol Version 5.0; this is due to the spiking with MTC in the placebo arm. Sensitivity analyses not applying this restriction will be provided.

Various imaging and clinical efficacy analyses will be handled differently for the FDA and European Medicines Agency (EMA). Summary statistics will be tabulated by visit and treatment group using observed data. ITT, E-MITT, MI-MITT, and PI-MITT population-weighted least squares means (LSM), unless otherwise stated, treatment differences, and 95% confidence intervals will also be included; the population will be determined by the corresponding model, dependent on whether the endpoint is an imaging endpoint or an efficacy endpoint. Where requested, annualized rates will be estimated based on the population-weighted LSM.

All models will include the randomization stratification variables as covariates unless otherwise stated. If the models do not converge because of too few observations for a given randomization stratification variable, the corresponding variable/variables will be removed from the model.

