#### 1.4. UK Versions of Study Protocol

The protocol (version 5.1, 05-FEB-2020) was adapted in response to requests made by the Medicines & Healthcare products Regulatory Agency (MHRA), after the inclusion of moderate AD subjects with protocol version 5.0.

The resulting first UK-specific version is protocol 5.2 UK (02-MAR-2020), which requires that subjects be either treatment naïve or to have already discontinued prior treatment with AChEI and/or memantine due to intolerance, lack of efficacy, or recommendation by the primary care provider prior to giving consent to participate in the study. The other major change is to require that the first visit in the newly

Sponsor:	TauRx Therapeutics Ltd.		
Protocol:	TRx-237-039		
Document Version No.:	3.0	Document Date:	07-JUN-2023

added open-label delayed-start period (after 2 weeks, V8) be an in-clinic visit rather than a telephone contact given that some subjects will be receiving HMTM treatment for the first time.

For all subsequent UK versions, no additional country specific changes were implemented.

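### The whole-brain annualized rate is the unscaled change from screening MRI to Week 52 (365 to 476 days on schedule), so per-arm yearly rates come out too high; the arm comparison is unaffected

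*SAP*

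**What the plan says.** The SAP's MRI estimand (5.9.1.4) takes as its patient-level outcome, at Week 52, the "Annualized rate, defined as the absolute change from Baseline, of whole brain atrophy". SAP 5.9.3.1 repeats that atrophy is the absolute change supplied by the imaging core laboratory, puts it into the MMRM, and obtains both the annualized rates and the arm difference from the least squares means (LSM). Protocol 17.4 allows this source: "annualized rates will be estimated based on the population-weighted LSM". Protocol 17.4.2 adds that time is to be continuous when an annualized rate is estimated, with nominal-time contrasts in support.

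Baseline is the screening scan. For subjects not on an AChEI or memantine, Protocol 15.3.3.2 places it on Days -63 to -1; for the others the section reads: "or Days -112 to -63 in subjects who begin Screening on an AChEI and/or memantine) will also be used as the baseline for volumetric measurements".

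In the second group a long lead is built into the design. Eligibility has to be documented, including "screening MRI and amyloid positive PET scan, before these drugs are discontinued" (Protocol Synopsis, Methodology), and Inclusion Criterion 9 then requires subjects to have been off these drugs "for at least 60 days at the time of the baseline assessments".

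SAP Table 5 sets Week 52 at Day 365. SAP 4.2 takes a year as 365.25 days.

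**The concern.** A rate per year needs a division by elapsed time, or a slope. The plan gives the name annualized to a total change over an interval that usually exceeds a year and differs between subjects. Per-arm annualized values are planned outputs for the first secondary endpoint (SAP 5.9.3.1, and the polynomial-time models in SAP 5.9.2.1). If the rule is followed as written, those values include atrophy from before the first dose.

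The excess is proportionally larger in a treated arm if the drug works, because the pre-dose atrophy is the same in both arms while the post-dose atrophy is smaller under treatment. Any percent slowing computed from the per-arm values would then be too small. Percent slowing is not a listed output, and the ADNI comparison mentioned in SAP 9 is described in another document that cannot be checked here, so neither is relied on below.

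**Working it through.** **Inputs**
- Study days (SAP 4.2): there is no Day 0. Day -k is k days before first dose; Day 365 is 364 days after it.
- Lead from screening MRI to first dose (Protocol 15.3.3.2): 1 to 63 days, or 63 to 112 days for subjects on an AChEI or memantine at the start of screening.
- Washout of at least 60 days (Inclusion Criterion 9), used below as the minimum lead in the second group.
- Assumptions: constant control atrophy and an on-schedule Week 52 scan.

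**The plan's own figure.** 52 × 7 + 1 = Day 365, as in SAP Table 5.

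**Span.** Shortest: 1 + 364 = 365 days. Where the two windows meet: 63 + 364 = 427. Longest: 112 + 364 = 476.

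**Overstatement in a control subject** = (364 + lead)/365.25 − 1:

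| Lead (days) | Span (days) | Excess |
|---|---|---|
| 1 | 365 | −0.1% |
| 32 (midpoint, not on drug) | 396 | +8.4% |
| 60 (washout alone) | 424 | +16.1% |
| 63 | 427 | +16.9% |
| 87.5 (midpoint, on drug) | 451.5 | +23.6% |
| 105 (Synopsis limit) | 469 | +28.4% |
| 112 | 476 | +30.3% |

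**Arm level.** The share p on an AChEI or memantine at screening is not given, so a range is shown. Mean lead = (1 − p) × first-group lead + p × second-group lead. For p = 0.5 at midpoints: 59.75 days, and (364 + 59.75)/365.25 = 1.160.

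| p | Midpoints (32 and 87.5 days) | Minimum leads (1 and 60 days) |
|---|---|---|
| 0 | +8.4% | −0.1% |
| 0.25 | +12.2% | +4.0% |
| 0.5 | +16.0% | +8.0% |
| 0.75 | +19.8% | +12.0% |
| 1 | +23.6% | +16.1% |

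A share of 1 is not realistic. Randomization is stratified by "prior use of standard AD treatment (two levels: AChEI/memantine or none", and UK subjects had to be untreated or "have already discontinued prior treatment with AChEI and/or memantine due to intolerance, lack of efficacy" before consent, among other permitted reasons (SAP 1.4).

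**Treated arm, illustrative 30% slowing from first dose.** Excess = (lead + 0.7 × 364)/(0.7 × 365.25) − 1. A lead of 32 days gives +12.2%; 87.5 days gives +33.9%. Slowing read from the LSMs at p = 0.5 would be 30% × (364/365.25)/1.160 = 25.8% at midpoints, or 30% × (364/365.25)/1.080 = 27.7% at minimum leads.

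**Arm difference.** The drug acts only over the 364 days after first dose, and the lead is complete before randomized treatment starts, so it cancels in expectation. A simulation checked this with 155 per arm, half on drug at screening and scan days uniform in their windows. With an assumed control rate of 13,000 mm³/year and a between-subject CV of 0.5, the mean control figure was about 15,090 (+16%). With 25% slowing the mean difference was −3,257, against an expected 0.25 × 13,000 × 364/365.25 = 3,239 in size. Type I error lay between 0.046 and 0.054 across the settings tried (control rate 6,500 or 13,000; CV 0.5 or 0.8).

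**Does the continuous-time code repair this?** No. Time runs from first dose (SAP 5.9.2.1), and the per-arm lines in the SAP 5.9.3.1 sample code evaluate the intercept plus 52 times the slope. The intercept absorbs the pre-dose atrophy. Take a true control rate of 1 per year and a mean lead of 59.75/365.25, about 0.163 years. The Week 52 LSM is then 1.16 while the slope is 1.00. With 30% slowing, intercept plus 52 weeks of slope returns 0.86, the same as the LSM, while the slope is 0.70.

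**The case against.** The strongest reply is that nothing inferential depends on this. The estimand's summary is the LSM difference, which is unbiased; the SAP states openly what it means by the term; and Protocol 17.4 permits LSM-based rates. All of that stands, and it is why the point is minor. It does not turn a total change over more than a year into a yearly rate.

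The size can also be disputed. The excess is about zero for a scan just before dosing, and the mean lead depends on a case mix and scan timing that the documents do not give. Midpoints may overstate the lead, since "MRI is the last of the key eligibility assessments to be scheduled" (Protocol 10.5.1.1). The upper end is not settled either: the Synopsis allows screening no earlier than 105 days before Visit 2, whereas Table 10-1 and Section 15.3.3.2 give Day -112. Those passages need reconciling; a 105-day limit would lower the maximum only to 469 days. In the other direction, a Visit 7 on Day 379 with the MRI 14 days later (Day 393, allowed by SAP 5.5) gives up to (392 + 63)/365.25 − 1 = +24.6% or (392 + 112)/365.25 − 1 = +38.0% in the two groups.

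Third, the sample code requests the fixed-effect solution, so the slope coefficients would probably be printed, and the code is marked for later validation. That is fair, but neither the SAP text nor the Week 52 estimate lines name the slope as the rate to report.

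Finally, a slope assumes linearity. That is a real cost and is taken up under the fix.

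**Conclusion.** The concern holds. As written, the rule gives per-arm annualized whole-brain atrophy values that are too high, and no other part of either document supplies the missing conversion. With constant control atrophy and on-schedule scans, the excess per control subject is 0 to 17% off AChEI/memantine at screening and 17 to 30% on it. For a control arm with 25 to 75% of subjects on these drugs at screening, it is 12 to 20% at window midpoints and 4 to 12% at minimum leads. Confidence is high about the missing scaling and its direction; the average size depends on the unreported share and scan timing. The absolute Week 52 arm difference and its test are unaffected in expectation. Severity: minor.

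**What to change.** - Rename the MMRM outcome as change from screening MRI at Week 52, and keep its unscaled arm difference as the test.
- Report the per-arm annualized rate as the post-dose slope from the continuous-time model in Protocol 17.4.2: the weekly time coefficient × 52.18 (365.25/7), without the intercept. State that atrophy is assumed roughly linear.
- Do not divide each subject's change by the scan interval for the arm comparison. That mixes untreated with treated time: in the simulation above it shrank the difference from −3,257 to about −2,826.
- When the sample code is validated, use the slope contrast. The present per-arm Week 52 lines also omit coefficients for severity, region and prior use, so they are not estimable as written.
- Apply the same rule to the temporoparietal and exploratory MRI rates.

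The cost is a few lines of SAP text and code, with no new data and no change to the main test. The downside is reliance on linearity. If control atrophy accelerates or decelerates by 20% per year, the slope misses the first-year change by +2.2% or −2.7%. If a 30% slowing begins only at Week 13, the treated slope is 0.70 against a true first-year change of 0.775, about 10% low. The slope should therefore remain descriptive.

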#### 5.9.1.5. PET Estimand (ITTv5)

The PET Estimand is designed to answer the question on the treatment effect of HMTM dose of 16 mg/day as monotherapy versus control (containing a small amount of MTC) in the targeted population of subjects with *very mild* AD (CDR of 0.5) at Week 52, regardless of trial product discontinuation, based

Sponsor:	TauRx Therapeutics Ltd.		
Protocol:	TRx-237-039		
Document Version No.:	3.0	Document Date:	07-JUN-2023

on the  $^{18}\text{F}$ -FDG-PET temporal lobe in SUVR. If data is available from subjects with other than a CDR of 0.5, these will not be included in the analysis.

This estimand is constructed in line with ICH E9 (R1) addendum. The five components defining the estimand of interest are:

- A. Treatment:** 52 weeks HMTM dose of 16 mg/day or matching control (containing a small amount of MTC) as monotherapy, regardless of adherence.
- B. Population:** Subjects with very mild AD (CDR of 0.5) and as further described by the inclusion and exclusion criteria, randomized under protocol version 5.0 or higher.
- C. Patient-level outcome / variable:** Change from Baseline of the  $^{18}\text{F}$ -FDG-PET temporal lobe in SUVR at Week 52.
- D. Population-level summary:** Population weighted least squares means difference.
- E. Intercurrent Events:** Identification of ICE is as described for the primary estimand (see Section 5.9.1.1).  
**Events 1** will be handled according to a hypothetical strategy as if patients have stayed on treatment.  
In a sensitivity analysis all these subject withdrawals are assumed to be potentially treatment-related, which are then handled using the treatment policy approach from ICE #2.  
**Events 2** will be handled using a treatment policy approach assuming that the subjects withdrawing from treatment for treatment-related reasons do not retain any treatment effect after Baseline; the intervention effect / in this case is  $I=E*(1-w)$ , where  $E$  is the treatment effect at Week 52 and  $w$  is the fraction of subjects within the HMTM treatment group who withdraw for potentially treatment-related reasons up to Week 52.  
**Events 3** will be handled according to the original randomized treatment group assuming they did not start AChEI and/or memantine and will be analyzed the same as ICE #2.  
**Events 4** will be handled according to a treatment policy strategy, using data after occurrence of the ICE. A sensitivity analysis will be carried out using the strategy as described for the ICE #2.

Sponsor:	TauRx Therapeutics Ltd.		
Protocol:	TRx-237-039		
Document Version No.:	3.0	Document Date:	07-JUN-2023

**Events 5, 6, and 7** will be handled according to a treatment policy approach, using all data (also after occurrence of respective ICE).

**Events 8** will be handled as treatment failure. If the patient dies prior to Week 52, the missing assessment at Week 52 will be imputed by the population average in decline within the control arm.

**Events 9, and 10** will be handled with a hypothetical strategy assuming COVID-19 disease would not have happened, not using data after occurrence of the ICE.

The PET Estimand (ITT) is defined as the PET Estimand, extending the population to the ITT population as done for the Primary estimand (ITT) (see Section 5.9.1.2).

